1.0 PROTOCOL SYNOPSIS

Name of Finished Product(s):	Fostamatinib Disodium (R935788)			
Title of Study: A Phase 3 Open Label Extension Study of Fostamatinib Disodium in the Treatment of Persistent/Chronic Immune Thrombocytopenic Purpura (ITP)				

Objectives:
 
 • The primary objective of this study is to assess the long term safety of fostamatinib in subjects with persistent/chronic ITP. • The secondary objectives of this study are to establish the long-term efficacy of fostamatinib in achieving and maintaining a stable platelet count in subjects who complete the treatment phase of Study C-935788-047 or Study C-935788-048, and to assess the pharmacokinetic (PK) profile of fostamatinib in subjects with persistent/chronic ITP. 				

Methodology:
 
This is a Phase 3 multicenter, open-label extension study to evaluate the long-term safety and the efficacy of fostamatinib in achieving and maintaining a stable platelet response in subjects with persistent/chronic ITP. The study will consist of monthly visits for 18 months followed by every-other-month visits for a maximum treatment duration of 5 years or until commercial availability of drug, whichever comes first.
 
Eligible subjects include subjects from Study C-935788-047 or C-935788-048 who have completed the Week 24 evaluation or who discontinue early (starting at Week 12) due to lack of response. All subjects will receive open-label fostamatinib.
 
Subjects designated as responders (defined as platelet count $\geq 50,000/\mu\text{L}$) at the time of rollover will continue at their current dose and regimen in the extension study. Subjects who enter the extension study as nonresponders (defined as platelet count $< 50,000/\mu\text{L}$) will be allocated to fostamatinib 100 mg PO bid regardless of their dose and regimen in Study C-935788-047 or C-935788-048. Subjects will remain blinded to their treatment assignment in Study C-935788-047 or C-935788-048 (active or placebo).
 
Treatment Allocation
 
 
  
Study C-935788-047 or C-935788-048
 
150 mg Fostamatinib or Placebo
 
100 mg Fostamatinib or Placebo
 	 
Responder
 
Non-Responder
 
Responder/Non-Responder
 	 
Study C-935788-049
 
150 mg Fostamatinib
 
100 mg Fostamatinib
 	
 
		
Study C-935788-047 or C-935788-048
 
150 mg Fostamatinib or Placebo
 
100 mg Fostamatinib or Placebo
	
Responder
 
Non-Responder
 
Responder/Non-Responder
	
Study C-935788-049
 
150 mg Fostamatinib
 
100 mg Fostamatinib


Study C-935788-047 or C-935788-048
 
150 mg Fostamatinib or Placebo
 
100 mg Fostamatinib or Placebo
	
Responder
 
Non-Responder
 
Responder/Non-Responder
	
Study C-935788-049
 
150 mg Fostamatinib
 
100 mg Fostamatinib
		

Subjects may continue to receive the concomitant medications for ITP that were allowed in the prior study (ie, glucocorticoids at dose less than equivalent of 20 mg prednisone daily, azathioprine or danazol). Subjects in whom the platelet count is stable at $\geq 50,000/\mu\text{L}$ may have the dose of concomitant medications for ITP gradually reduced according to standard practice.

At the end of Month 1 (approximately Day 30), subjects receiving fostamatinib 100 mg PO *bid* should have the dose escalated to fostamatinib 150 mg PO *bid* if platelet count $< 50,000/\mu\text{L}$ and the study drug is well tolerated (refer to [Section 7.2.1](#)). Conversely, the dose may be reduced at any time to a dose as low as fostamatinib 100 mg PO *qd* if dose-limiting AEs are observed as defined by this protocol.

Certain therapeutic regimens for ITP will be permitted for subjects with platelet counts $< 50,000/\mu\text{L}$ who need “rescue” support of the platelet count. Allowed therapeutic regimens include:

- IVIg: up to 1 g/kg x 1-3 days, or
- IV anti-D: up to 50-75 $\mu\text{g}/\text{kg}$ x 1-2 days, or
- IV methylprednisolone up to 1 g/day x 1-3 days or oral dexamethasone up to 40 mg/day x 1-2 days or oral prednisone up to 1 mg/kg/day x 1-3 days.

At Month 2, blood samples for PK analysis will be collected from a subset of 12 subjects at selected sites. Subjects will remain at the clinic for up to 9 hours during the visit. When a subject arrives at the clinic, the time of the last dose of fostamatinib will be recorded in the eCRF.

Samples (4 mL) of whole blood will be collected at the following time points: predose and 0.5, 1, 2, 4, 6, and 8 hours post-dose.

Number of Subjects: Up to 150 subjects will be enrolled at multiple sites.

Study Population: Patients with persistent/chronic ITP. For the purpose of this study, the term ‘subject’ will refer to patients with persistent/chronic ITP participating in this study.

Inclusion Criteria:

1. Subject must be willing and able to give written informed consent by signing an IRB-approved Informed Consent Form prior to participating in any study-specific procedures.
2. Subjects must have completed the Week 24 evaluation of Study C-935788-047 or C-935788-048 or have discontinued early (starting at Week 12) due to lack of response. No more than 7 days may have elapsed between the last day of treatment on Study C-935788-047 or C-935788-048 and the initial dosing (Day 1) in Study C-935788-049.

3. Male or female at least 18 years of age.
4. Females must be either post-menopausal for at least 1 year or surgically sterile; or if female of child-bearing potential, must not be pregnant or lactating and must agree to use an acceptable method of birth control throughout the duration of the trial and for 30 days following the last dose. Acceptable methods of birth control are defined as: hormonal contraception (pill, injection or implant) used consistently for at least 30 days prior to enrollment, intrauterine device (IUD), double-barrier (ie, condom and spermicide, or condom and diaphragm), or complete abstinence.
5. In the Investigator's opinion, the subject has the ability to understand the nature of the study and any hazards of participation and to communicate satisfactorily with the Investigator.

Exclusion Criteria:

1. Any subject who discontinued participation in Study C-935788-047 or C-935788-048 prior to Week 12 or for any reason other than lack of response. Exceptions may be considered on a case-by-case basis after consultation between the Investigator and Sponsor with the specific reason for the exception noted.
2. Subjects with poorly controlled hypertension during Study C-935788-047 or C-935788-048, defined as persistent or repeated systolic ≥ 140 mmHg, or diastolic ≥ 90 mmHg whether or not the subject is receiving anti-hypertensive treatment.
3. Subjects with the following laboratory abnormalities at the time of enrollment (Day 1): a leukocyte count $< 2,000/\mu\text{L}$, a neutrophil count (ANC) of $< 1,000/\mu\text{L}$, lymphocyte count $< 750/\mu\text{L}$, Hgb < 10 g/dL, or transaminase levels (ALT, AST) > 1.5 x ULN, bilirubin > 1.5 x ULN, or estimated glomerular filtration rate (eGFR) < 30 mL/min.
4. Subjects who have a significant infection, an acute infection such as influenza, or known inflammatory process at the time of enrollment into this study.
5. Subjects who have received any blood or blood products within the 2 weeks prior to enrollment (IVIg or anti-D are allowed if used for rescue therapy).

Investigational Product: Fostamatinib disodium (R935788) 100 mg and 150 mg tablets

Route of Administration: Oral

Dose: The initial dose will be 100 mg fostamatinib PO *bid* daily.

At the end of Month 1, subjects who have initiated dosing at fostamatinib 100 mg PO *bid* in this extension study (and who have not previously had a dose reduction) should have their dose increased to fostamatinib 150 mg PO *bid* if the platelet count remains below $50,000/\mu\text{L}$ and the study drug has been well tolerated.

Treatment with fostamatinib has been associated with adverse events (AEs) that may require temporary interruption of the study drug and/or a reduction in study drug dose. Modification of study drug administration may be required.

Duration of Treatment: A maximum of 5 years or until fostamatinib becomes commercially available, whichever comes first.

Statistical Methods:

Analysis Populations:

a. Treated Population

The Treated population will include all enrolled and treated subjects. All efficacy endpoints will be analyzed based on the Treated population, and subjects will be analyzed according to their actual treatment. The efficacy analyses based on the Treated population will be considered the primary efficacy analyses. All analyses of safety will also be performed on the Treated Population.

b. Per-Protocol Population

The Per-Protocol (PP) population will include all subjects in the Treated population who had no major protocol violations in either study

All efficacy endpoints will also be analyzed based on the PP population, and subjects will be analyzed according to their actual treatment. The analyses based on the PP population will be considered secondary analyses of efficacy.

Primary Efficacy Endpoint:

Version 1: The first version of the primary efficacy endpoint is for the purpose of assessing efficacy among all patients while they are on active treatment in one of the prior studies, in the current extension study, or in both. This version of the primary efficacy endpoint is the achievement and maintenance of a stable platelet count defined as follows:

- 1) Achievement of a platelet count of at least 50,000/ μ L within 12 weeks of beginning active treatment.
- 2) Achievement of a sustained stable platelet response; defined as no two visits, at least 4 weeks apart, with a platelet count < 50,000/ μ L, without an intervening visit with a platelet count of \geq 50,000/ μ L unrelated to rescue therapy, within a period of 12 months following initial achievement of the target platelet count (see above).

The beginning of active treatment may be in the prior study or in the present extension study, depending upon when the subject first received active treatment. Subjects who discontinue treatment due to lack of efficacy or to an AE prior to 12 months following achievement of a platelet count of at least 50,000/ μ L will be considered failures. This endpoint will be summarized using counts and percentages, together with a 95% exact (Clopper-Pearson) confidence interval (CI) for the true percentage.

Version 2: The second version of the primary efficacy endpoint is for the purpose of a within-subject, between-study comparison of fostamatinib and placebo among subjects randomized to placebo in either of the prior studies. This version of the primary efficacy endpoint is the achievement and maintenance of a stable platelet count defined as follows:

- 1) Achievement of a platelet count of at least 50,000/ μ L within 12 weeks of beginning treatment (placebo treatment in the prior study and fostamatinib treatment in the present study) and
- 2) Achievement of a sustained stable platelet response; defined as no two visits, at least 4 weeks apart, with a platelet count < 50,000/ μ L, without an intervening visit with a platelet count of \geq 50,000/ μ L unrelated to rescue therapy, within a period of 12 weeks following initial achievement of the target platelet count (see above).

Subjects who discontinue treatment due to lack of efficacy or to an AE prior to 12 weeks following achievement of a platelet count of at least 50,000/ μ L, will be considered failures. The null and alternative hypotheses for the comparison of fostamatinib vs. placebo are as follows:

$$H_0: p_F = p_P \quad \text{vs.} \quad H_1: p_F \neq p_P$$

where p_F and p_P denote the true proportions achieving and maintaining a stable platelet count for fostamatinib and placebo, respectively. The null hypothesis will be tested using a 2-sided McNemar's test conducted with a significance level of 0.05.

Secondary Efficacy Endpoints:

The secondary efficacy endpoints are as follows:

- Duration of stable platelet response.
- Proportion of subjects in whom a reduction in the dose of concomitant ITP therapy can be achieved while maintaining an adequate platelet count.

The duration of stable platelet response will be analyzed using the Kaplan-Meier method, and the Kaplan-Meier estimate of the median duration of stable platelet response will be presented together with the 95% CI for the true median.

Achieving a reduction in the dose of concomitant ITP therapy while maintaining an adequate platelet count will be summarized using counts and percentages and a 95% exact (Clopper-Pearson) CI for the true percentage. A two-sided, McNemar's test will be performed to compare the proportions of successes between the fostamatinib and placebo treatments.

Safety Endpoints:

The safety outcomes of this study include the frequency and severity of bleeding according to the IBLS, the change from baseline in blood pressure, liver function, and ANC; the incidence of GI complaints; infection; and overall AEs.

Pharmacokinetic Endpoints:

Pharmacokinetic parameters to be estimated for the major metabolite R406 include maximum plasma concentration (C_{max}), time to C_{max} (T_{max}), and area under the plasma concentration-time curve through 8 hours ($AUC_{(0-8)}$). C_{max} and T_{max} will be taken directly from the data;

AUC₍₀₋₈₎ will be calculated using the linear trapezoidal method. These PK parameters will be summarized using descriptive statistics.

Determination of Sample Size:

The sample size will be based upon the number of subjects in the C-935788-047 and C-935788-048 studies who are eligible to participate in this study and who choose to participate.

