3.6 Safety

A number of Phase 2 and 3 studies of fostamatinib have been conducted in several indications including ITP, RA and B- and T-cell lymphomas. Doses of fostamatinib have ranged from 50 to 250 mg PO *bid*, depending on the indication being treated. The majority of patients have been treated at doses ranging from 50-150 mg PO *bid*.

The overall pattern of adverse effects of fostamatinib in these various clinical settings (patients

with RA, severely ill patients with lymphoma and advanced solid tumors, chronically ill patients with ITP, and in healthy subjects), has been consistent, and includes dose-dependent effects on blood pressure (BP), ANC, dizziness, gastrointestinal (GI) complaints and liver function test abnormalities, all of which are reversible and manageable with appropriate safety monitoring (Table 1). The ITP patients (on no anti-metabolites or chemotherapy) have not manifested neutropenia, despite receiving higher doses of fostamatinib than the RA patients. The lymphoma patients have experienced more cytopenias, and infections, consistent with their extensive pre-treatment and underlying disease. In patients with solid tumors, the overall pattern of reported AEs was consistent with a population of heavily pretreated, relapsed patients with solid tumors of varying histologies.

**Table 1: Frequent Adverse Events
(Pooled Data - Phase 3 Placebo-Controlled RA Studies)**

Sign/Symptom	Fostamatinib		Placebo N = 715 254 PY
	100 mg bid N = 723 288 PY	100 mg bid (1 month) followed by 150 mg qd N = 710 277 PY	
BP > 140/90	333 (46%)	315 (44%)	170 (24%)
BP > 160/100	66 (9%)	63 (9%)	24 (3%)
Diarrhea	94 (33%)	112 (40%)	32 (13%)
Nausea	36 (13%)	41 (15%)	17 (7%)
Dizziness	18 (6%)	12 (4%)	5 (1%)
Abdominal Pain*	39 (14%)	38 (14%)	27 (11%)
ALT/AST \geq 3 x ULN	38 (5%)	37 (5%)	17 (2%)
PMN < 1500/ μ L	66 (9%)	41 (6%)	8 (1%)

ALT= Alanine aminotransferase, AST = Aspartate aminotransferase, BP = Blood pressure, PY = Patient years, PMN = Polymorphonuclear leukocytes, ULN = Upper limit of normal

* Represents various verbatim terms

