6.2 Exclusion Criteria

1. Any subject who discontinued participation in Study C-935788-047 or C-935788-048 prior to Week 12 or for any reason other than lack of response. Exceptions may be considered on a case-by-case basis after consultation between the Investigator and Sponsor with the specific reason for the exception noted.
2. Subjects with poorly controlled hypertension during Study C-935788-047 or C-935788-048, defined as persistent or repeated systolic ≥ 140 mmHg, or diastolic ≥ 90 mmHg whether or not the subject is receiving antihypertensive treatment.
3. Subjects with the following laboratory abnormalities at the time of enrollment (Day 1): a leukocyte count $< 2,000/\mu\text{L}$, an ANC of $< 1,000/\mu\text{L}$, lymphocyte count $< 750/\mu\text{L}$, Hgb < 10 g/dL, or transaminase levels (ALT, AST) > 1.5 x ULN, bilirubin > 1.5 x ULN, or estimated glomerular filtration rate (eGFR) < 30 mL/min.
4. Subjects who have a significant infection, an acute infection such as influenza, or known inflammatory process at the time of enrollment into this study.
5. Subjects who have received any blood or blood products within the 2 weeks prior to enrollment (IVIg or anti-D are allowed if used for rescue therapy).

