Appendix 4: Management of Hypertension

Treatment with fostamatinib may cause blood pressure elevation in certain subjects. It is believed that this effect is a result of off-target activity against the VEGFR2 receptor. Increases in BP have proven to be amenable to treatment, generally without a requirement for study drug interruption. **Subjects with elevated blood pressure should receive prompt treatment.**

Blood pressure for all subjects should be kept below 140/90 mmHg; for subjects with increased cardiovascular risk, diabetes or renal insufficiency consideration should be given to maintaining the blood pressure below 130/80 mmHg.

In previous clinical studies evaluating fostamatinib, the following antihypertensive agents have proven effective in managing BP:

- Calcium channel blockers
- Angiotensin converting enzyme inhibitors
- Angiotensin receptor blockers
- Beta-blockers

If aggressive and appropriate anti-hypertensive therapy does not control BP (< 140/90), it may be necessary to reduce the dose of study medication.

Management Algorithm for Elevated Blood Pressure

Follow the dose adjustment guidelines below when adjusting the dose of study medication.

Dose Adjustment

Dose	Dose Level -1	Dose Level -2	Dose Level -3 ^a	Dose Level -4 ^a
100 mg PO bid	150 mg PO qd	100 mg PO qd	discontinue	----
150 mg PO bid	100 mg PO bid	150 mg PO qd	100 mg PO qd	discontinue

^a The Sponsor's Medical Monitor should be consulted prior to consideration of dose modification to levels -3 or -4.

The following should result in prompt discontinuation of study medication:

- The subject becomes symptomatic due to blood pressure elevation.
- The blood pressure cannot be brought under control despite best efforts at blood pressure management.

If BP > 180/110 mmHg at any time after randomization:

- Immediately interrupt study drug administration.
- Initiate or increase anti-hypertensive medication.
- Reassess BP twice weekly.
- If repeat BP \geq 180/110 mmHg despite anti-hypertensive treatment, discontinue study drug.
- Increase anti-hypertensive medications until control is established.
- Restart study drug when blood pressure < 140/90 mm Hg.

If the BP is found to be 160-179 systolic or 100-109 diastolic at any visit after randomization:

- Continue study drug at assigned dose level.
- Initiate or increase anti-hypertensive therapy immediately.
- Reassess BP twice weekly.

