- If, after 1 week, the BP remains \geq 160-179 systolic or \geq 100-109 diastolic despite aggressive antihypertensive therapy, interrupt study drug administration.
- Increase anti-hypertensive medications until control is established.
- Restart study drug when blood pressure < 140/90 mmHg.

If BP is \geq 140 mmHg systolic and/or \geq 90 mmHg diastolic but below 160 systolic or 100 diastolic at any visit after randomization:

- Continue study drug at assigned dose level.
- Repeat blood pressure assessment within 1 week.
- If blood pressure remains above \geq 140 mmHg systolic and/or \geq 90 mmHg diastolic after 1 week initiate or increase antihypertensive therapy immediately.
- Continue to monitor BP weekly until control is established.
- If BP remains \geq 140 mmHg systolic and/or \geq 90 mmHg diastolic for more than 8 weeks, despite aggressive antihypertensive therapy, reduce dose of study drug to dose level -1.

Source: Maitland 2010 ⁽⁸⁾

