## **7.0 PATIENT DISPOSITION**

The number of patients signing the informed consent, screen failures, and patients in the Treated Population will be presented. The numbers and percentages of patients who discontinued from the study at the time of database lock, along with the reason for discontinuation, will be also be presented.

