### 11.3 Vital Signs

Descriptive statistics will be presented by scheduled visit for the actual values and the changes and percentage changes from baseline for each vital sign. The maximum post baseline systolic blood pressure categories ( $< 140$  mmHg,  $140 - < 160$  mmHg,  $160 - < 180$  mmHg and  $\geq 180$  mmHg) will be summarized using counts and percentages. This analysis will also be performed by baseline use of anti-hypertensives (yes/no). The anti-hypertensives are the medications with any of the following ATC codes at baseline: C02 (anti-hypertensives), C03 (diuretics), C04 (peripheral vasodilators), C07 (beta blocking agents), C08 (calcium channel blockers), and C09 (agents acting on the rennin-angiotensin system). These analyses will be repeated for maximum post baseline diastolic blood pressure categories ( $< 90$  mmHg,  $90 - < 100$  mmHg,  $100 - < 110$  mmHg and  $\geq 110$  mmHg).

The number and percentage of following types of patients will be presented:

- Patients with systolic BP  $\geq 140$  mmHg or diastolic BP  $\geq 90$  mmHg at consecutive visits (2 or more visits, 3 or more visits) of present study
- Patients with systolic BP  $\geq 140$  mmHg or diastolic BP  $\geq 90$  mmHg anytime during the post-baseline of present study
- Patients with systolic BP  $\geq 160$  mmHg or diastolic BP  $\geq 100$  mmHg at consecutive visits (2 or more visits, 3 or more visits) of present study
- Patients with systolic BP  $\geq 160$  mmHg or diastolic BP  $\geq 100$  mmHg anytime during the post-baseline of present study
- Patients with systolic BP  $\geq 180$  mmHg or diastolic BP  $\geq 110$  mmHg at consecutive visits (2 or more visits, 3 or more visits) of present study
- Patients with systolic BP  $\geq 180$  mmHg or diastolic BP  $\geq 110$  mmHg anytime during the post-baseline of present study

In addition, shifts based on new guidance in blood pressure (**Appendix 14.3**) from normal, elevated, Stage 1, Stage 2 and hypertensive crisis at baseline to normal, elevated, Stage 1, Stage 2 and hypertensive crisis for the maximum observed value, and the last value post baseline will

be tabulated. The maximum observed blood pressure and the last blood pressure post baseline will be based on both scheduled and unscheduled visits.

Box plots indicating mean and median as well as the 25th and 75th percentiles, reference plots, and spaghetti plots will be presented by scheduled visit for both raw values and changes from baseline.

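### SAP 11.3 pools prior-fostamatinib subjects, who entered on the strength of their on-drug blood pressure, with prior-placebo subjects, who were screened off drug; the blood pressure tables should be split by prior study treatment group

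*Protocol*

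**What the plan says.** **Entry.** Protocol 6.2, criterion 2, excludes "Subjects with poorly controlled hypertension during Study C-935788-047 or C-935788-048". The synopsis gives the same definition: "defined as persistent or repeated systolic ≥ 140 mmHg, or diastolic ≥ 90 mmHg whether or not the subject is receiving anti-hypertensive treatment". Persistent or repeated readings each suffice. The criterion gives no number of readings, no window within the parent study, and no reference to BP at rollover. Criterion 3, by contrast, ties its laboratory limits to Day 1.

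**Drug effect.** Protocol 3.6 lists "dose-dependent effects on blood pressure (BP), ANC, dizziness, gastrointestinal (GI) complaints and liver function test abnormalities" as a consistent pattern across indications. Section 3.6.1 adds that BP increases generally came early and that a history of hypertension raised the risk. Long-term safety is the primary objective (Protocol 4.1), and BP change is a named safety endpoint (4.4).

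**Management in the extension.** Appendix 4 says "Increases in BP have proven to be amenable to treatment, generally without a requirement for study drug interruption". For readings from 140/90 up to 160/100 its first step is "Continue study drug at assigned dose level". Antihypertensive therapy follows if BP is still raised after a week, and a one-level dose reduction follows only after more than 8 weeks despite therapy. The higher tiers interrupt drug, and symptomatic or uncontrollable BP leads to discontinuation.

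**Analysis.** SAP 5.1 restricts analyses to extension data apart from baseline and a few exceptions; the exceptions it names concern platelets and efficacy. For the maximum-BP categories SAP 11.3 adds one breakdown: "This analysis will also be performed by baseline use of anti-hypertensives (yes/no". The counts above each BP threshold and the shift tables have no breakdown. SAP 7.0 says "The number of patients signing the informed consent, screen failures, and patients in the Treated Population will be presented", with no reason for screen failure and no prior arm.

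**The concern.** One entry criterion does two different things. For a prior-fostamatinib subject it asks whether BP rose repeatedly while taking the drug under study. For a prior-placebo subject it asks whether BP was repeatedly high without the drug. Those who pass are, in the first group, people who have already shown up to 24 weeks without repeated elevation on drug. In the second group they are people whose BP response to the drug is still unknown.

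A hypertension rate pooled over the two answers neither of the questions a safety reader would ask: how often BP rises when the drug is started, and how often it rises later in those who stay on it. Increases generally come early, and the parent-study readings of prior-fostamatinib subjects are not counted in the extension's maximum-BP tables. The pooled rate is therefore likely to fall below the first-exposure rate. No planned BP table would let a reader see this.

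**Working it through.** **1. Reproduce the protocol's figures.** Protocol Table 1 (pooled phase 3 rheumatoid arthritis studies), BP above 140/90:

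- 100 mg bid: 333/723 = 46.1% (stated 46%)
- 100 mg bid for 1 month, then 150 mg qd: 315/710 = 44.4% (stated 44%)
- placebo: 170/715 = 23.8% (stated 24%)

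Risk ratios against placebo are 46.1/23.8 = 1.94 and 44.4/23.8 = 1.87. Mean follow-up was 288/723 × 52.18 = 20.8 weeks on 100 mg bid and 254/715 × 52.18 = 18.5 weeks on placebo, somewhat shorter than the 24-week parent studies.

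**2. How unequal could the selection be?** Let f be the share of those crossing 140/90 who had repeated readings. The documents give no value, so it is varied and, for now, taken as equal in both arms. Share barred = f × ever-rate.

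| f (assumed) | Fostamatinib | Placebo |
|---|---|---|
| 25% | 11-12% | 6% |
| 50% | 22-23% | 12% |
| 100% | 44-46% | 24% |

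If f differs by arm, the barred proportions become equal only when placebo crossers are about 1.9 times as likely as fostamatinib crossers to have repeated readings.

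**3. Which arm would the barred subjects come from?** With r the parent allocation ratio (fostamatinib to placebo, not in the documents), the fostamatinib share is r × 0.461 / (r × 0.461 + 0.238):

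- 1:1 gives 66%
- 2:1 gives 79%
- 1:2 gives 49%

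Not all of this is drug effect. The excess fraction among fostamatinib crossers is (46.1 − 23.8)/46.1 = 48%, so about half of those crossings would be expected on placebo. Crossings in excess of the placebo rate are 32% of all crossers at 1:1 and 38% at 2:1.

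**4. What pooling does.** Let C and F be the extension hypertension rates in continuers and in first-exposure subjects, and w the continuers' share of the cohort. The pooled rate is wC + (1 − w)F, so it falls short of F by w(F − C). Applying step 2, w = r(1 − 0.461f) / [r(1 − 0.461f) + (1 − 0.238f)]:

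| Allocation | f = 25% | f = 50% | f = 100% |
|---|---|---|---|
| 1:1 | 0.485 | 0.466 | 0.414 |
| 2:1 | 0.653 | 0.636 | 0.586 |

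Over w = 0.414 to 0.653, an assumed gap F − C of 5, 10 or 20 points gives a shortfall of 2.1-3.3, 4.1-6.5 or 8.3-13.1 points. The gap is illustrative, and w ignores every other reason for not rolling over. Only the split tables would show the real values.

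**5. Is the split already used elsewhere?** Yes: for hypertension interventions (SAP 5.7), platelet counts (10.3), bleeding scales (11.4) and rescue therapy (12.5). The maximum-BP summary in 5.7 sits directly above the hypertension interventions and lacks it.

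**The case against.** Several stronger readings are tempting, and the documents do not support them.

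- **Exclusion 2 and Appendix 4 contradict each other.** One governs entry and the other governs enrolled subjects, and such rules may differ. The protocol does the same for liver tests: entry is barred above 1.5 × ULN, while Appendix 1 acts from 3 × ULN for transaminases. Only the lowest tier of Appendix 4 keeps drug going throughout. What stands is a difference in how one 140-159/90-99 course is treated, made harder to apply because "repeated" is undefined.
- **Drug-induced hypertension is barred from the cohort.** Only repeated elevation in the parent study is barred. Single elevations pass, later onset can still be observed, prior-placebo subjects meet the drug for the first time in the extension, and Protocol 11.4 allows exemptions.
- **The losses fall mostly in one prior arm.** This is inferred from rheumatoid arthritis patients, from any crossing of 140/90, with allocation unknown.
- **The prior-placebo group is unscreened.** It faced the same criterion, off drug. Since a history of hypertension raises risk, its first-exposure rate may also be low relative to an unscreened population.
- **The share of retained subjects who had ever crossed 140/90 is the bias in the extension.** That figure describes the parent-study past, not an extension rate over up to 60 months.

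Existing handling also counts. SAP 5.8 sets baseline before the first fostamatinib dose, so change scores and shifts have a pre-drug reference, and listings are sorted by prior arm. That neither restores excluded subjects nor separates the groups in the maximum-BP categories and threshold counts. Finally, SAP 5.4 reports an interim analysis already performed and SAP 3.5 describes rollover in the past tense. Entry was probably over, and rewording the criterion may not alter the cohort.

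**Conclusion.** The point holds as a reporting gap under the primary objective. Exclusion 2 selects the two prior arms on different quantities, and SAP 11.3 pools them without showing it. The pooled hypertension rates are likely to understate the BP effect. That direction rests on two things: prior-fostamatinib subjects were admitted after on-drug screening, and BP increases generally occur early.

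The size cannot be fixed from the documents. If 25% to 100% of crossers had repeated readings, the criterion would bar about 11-46% of fostamatinib and 6-24% of placebo candidates. Those ranges assume that rheumatoid arthritis rates carry over to ITP and that the share with repeated readings is similar in both arms. The parent-study allocation is not given either.

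The documents do not support saying that the cohort excludes drug-induced hypertension, that the losses lie mainly in one arm, or that the two BP rules directly contradict each other.

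**What to change.** - **SAP 11.3, and the maximum-BP summary in 5.7:** present the BP categories, threshold counts and shift tables by prior study treatment group and overall, as already planned for hypertension interventions, platelets, bleeding and rescue.
- **Interpretation, stated in the SAP:** describe the prior-placebo group as first exposure, noting that it too was screened under Exclusion 2, on off-drug BP. State that the prior-fostamatinib group was selected on on-drug BP.
- **SAP 7.0:** where reasons for non-entry were recorded, report screen failures due to Exclusion 2 by prior arm. Subjects who never consented may not be recoverable.
- **Protocol:** reconcile Exclusion 2 (synopsis and 6.2) with the lowest tier of Appendix 4, which treats the same 140-159/90-99 course differently. No threshold or clinical rule is proposed here.

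The cost is smaller cells per table, with at most 150 subjects planned in all. The BP changes need no new data collection, only a by-group column that the SAP already uses elsewhere.
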